**Table 1. Ibrutinib/Placebo Dose Modifications**

Occurrence	Action to be Taken
First	Withhold study drug until recovery to Grade $\leq$ 1 or baseline; may restart at original dose level
Second	Withhold study drug until recovery to Grade $\leq$ 1 or baseline; may restart at 1 dose level lower (eg, 280 mg/day for 420 mg/day dose)
Third	Withhold study drug until recovery to Grade $\leq$ 1 or baseline; may restart at 1 dose level lower (eg, 140 mg/day for 420 mg/day dose)
Fourth	Discontinue study drug

**Table 2. Ibrutinib/Placebo Dose Reduction Levels**

Starting Dose Level	420 mg	280 mg	140 mg
Dose Reduction Level 1	280 mg	140 mg	70 mg
Dose Reduction Level 2	140 mg	70 mg	Discontinue
Dose Reduction Level 3	Discontinue	Discontinue	--

For required dose modification for hepatic impairment refer to [Section 5.3.1.5](#) and for concomitant treatment with CYP3A inhibitors refer to [Section 6.2.1](#).

**5.3.1.5. Dose Modification for Subjects with Hepatic Impairment**

Dose modifications for hepatic impairment will depend on baseline total bilirubin level and subsequent changes in bilirubin levels per [Table 3](#) below. If the elevation of bilirubin is due to a non-hepatic cause or Gilbert's Syndrome, then no dose modifications are necessary.

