	
failure as defined by the New York Heart Association Functional Classification; or a history of myocardial infarction, unstable angina, or acute coronary syndrome within 6 months prior to randomization.
 
 
7. Any uncontrolled active systemic infection or active infection requiring systemic treatment that was ongoing <math>\leq 7</math> days before randomization. This does not include secondary prophylaxis of well controlled fungal infections, ongoing treatment of controlled viral reactivations (eg, CMV), or treatment or prophylaxis of controlled low-grade central line infections (eg, Staphylococcus epidermidis).
 
8. Progressive underlying malignant disease or active post-transplant lymphoproliferative disease.
 
9. History of other malignancy (not including the underlying malignancy that was the indication for transplant), with the following exceptions: 
 
• Malignancy treated with curative intent and with no evidence of active disease present for more than 3 years prior to Screening and felt to be at low risk for recurrence by treating physician
 
• Adequately treated nonmelanomatous skin cancer or lentigo maligna melanoma without current evidence of disease
 
• Adequately treated cervical carcinoma in situ without current evidence of disease
 
 
 
10. Subject has a concurrent illness which in the opinion of the investigator may interfere with the treatment and evaluation of the subject.
 
11. Known bleeding disorders (eg, von Willebrand's disease or hemophilia).
 
12. History of stroke or intracranial hemorrhage within 6 months prior to randomization.
 
13. Known history of human immunodeficiency virus (HIV).
 
14. Subject with chronic liver disease with hepatic impairment per Child-Pugh classification Class C (Appendix E). Please note that acute liver dysfunction due to cGVHD is not applicable to the evaluation of Child-Pugh classification.
 
15. Active hepatitis C virus (HCV) or hepatitis B virus (HBV). Subjects who are positive for hepatitis B core antibody or hepatitis B surface antigen or hepatitis C antibody must have a negative polymerase chain reaction (PCR) result before randomization. Those who are PCR positive will be excluded.
 
16. Vaccinated with live, attenuated vaccines within 4 weeks of randomization.
 
17. Major surgery within 4 weeks of randomization.
 
18. Any life-threatening illness, medical condition, or organ system dysfunction that, in the investigator's opinion, could compromise the subject's safety or put the study outcomes at undue risk.
 
19. Unable to swallow capsules or malabsorption syndrome, disease
 

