##### **1.2.2.1. Pharmacokinetics and Product Metabolism**

Following oral administration of ibrutinib at doses ranging from 420 to 840 mg/day, exposure to ibrutinib increased proportionally to doses increased with substantial intersubject variability. The mean half-life ( $t_{1/2}$ ) of ibrutinib ranged from 4 to 13 hours, with a median time to maximum plasma concentration ( $T_{max}$ ) of 2 hours. Taking into account the approximate doubling in mean systemic exposure when dosed with food and the favorable safety profile, ibrutinib can be dosed with or without food. Ibrutinib is extensively metabolized primarily by cytochrome P450 (CYP) 3A4 enzymes. The on-target effects of metabolite PCI-45227 are not considered clinically relevant. Steady-state exposure of ibrutinib and PCI-45227 was less than 2-fold of single dose exposure. Less than 1% of ibrutinib is excreted renally. Ibrutinib exposure is not

altered in patients with creatinine clearance (CrCl) >30 mL/min. Patients with severe renal impairment or patients on dialysis have not been studied. Following single dose administration, the AUC of ibrutinib increased 2.7-, 8.2- and 9.8-fold in subjects with mild (Child-Pugh class A), moderate (Child-Pugh class B), and severe (Child-Pugh class C) hepatic impairment compared to subjects with normal liver function. A higher proportion of Grade 3 or higher adverse reactions were reported in patients with B-cell malignancies (CLL, MCL and WM) with mild hepatic impairment based on NCI organ dysfunction working group (NCI-ODWG) criteria for hepatic dysfunction compared to patients with normal hepatic function. In the Phase 2 study in subjects with cGVHD, there were no differences in ibrutinib exposure between subjects with normal (n=29) and mild hepatic impairment based on baseline liver function test per NCI criteria (n=13).

For the most comprehensive information regarding pharmacokinetics (PK) and product metabolism, please refer to the current version of the [IB](#).

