#### *Laboratory*

9. Adequate renal function defined as estimated Creatinine Clearance  $\geq 30$  mL/min (Cockcroft-Gault formula)
10. Adequate hepatic function as defined by:
  - Total bilirubin of  $\leq 1.5$  x ULN (unless of non-hepatic origin or due to Gilbert's Syndrome) or
  - Total bilirubin of  $> 1.5$  x ULN to 3.0 x ULN if due to GVHD
11. Adequate hematological function defined as:
  - Absolute neutrophil count  $\geq 1.0 \times 10^9/L$  and off growth factor support for 7 days
  - Platelets  $\geq 30 \times 10^9/L$  and no transfusion for 7 days
12. PT/INR  $< 1.5$  x ULN and PTT (aPTT)  $< 1.5$  x ULN (unless abnormalities are unrelated to coagulopathy or bleeding disorder). When treated with warfarin or other vitamin K antagonist, then INR  $\leq 3.0$  ([Section 6.2.3](#)).

---

*Ethical/Other*

13. Male and female subjects of reproductive potential who agree to use both a highly effective methods of birth control (eg, implants, injectables, combined oral contraceptives, some intrauterine devices [IUDs], complete abstinence, or sterilized partner) and a barrier method (eg, condoms, cervical ring, sponge, etc.) during the period of therapy and for 90 days for both females and males after the last dose of study drug.

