- Malignancy treated with curative intent and with no evidence of active disease present for more than 3 years prior to Screening and felt to be at low risk for recurrence by treating physician
  - Adequately treated nonmelanomatous skin cancer or lentigo maligna melanoma without current evidence of disease
  - Adequately treated cervical carcinoma in situ without current evidence of disease
10. Subject has a concurrent illness which in the opinion of the investigator may interfere with the treatment and evaluation of the subject.
  11. Known bleeding disorders (eg, von Willebrand's disease or hemophilia).
  12. History of stroke or intracranial hemorrhage within 6 months prior to randomization.
  13. Known history of human immunodeficiency virus (HIV).
  14. Subjects with chronic liver disease with hepatic impairment per Child-Pugh classification Class C ([Appendix E](#)). Please note that acute liver dysfunction due to cGVHD is not applicable to the evaluation of Child-Pugh classification.
  15. Active hepatitis C virus (HCV) or hepatitis B virus (HBV). Subjects who are positive for hepatitis B core antibody or hepatitis B surface antigen or hepatitis C antibody must have a negative polymerase chain reaction (PCR) result before randomization. Those who are PCR positive will be excluded.
  16. Vaccinated with live, attenuated vaccines within 4 weeks of randomization.
  17. Major surgery within 4 weeks of randomization.
  18. Any life-threatening illness, medical condition, or organ system dysfunction that, in the investigator's opinion, could compromise the subject's safety or put the study outcomes at undue risk.
  19. Unable to swallow capsules or malabsorption syndrome, disease significantly affecting gastrointestinal function, or resection of the stomach or small bowel, symptomatic inflammatory bowel disease or ulcerative colitis, or partial or complete bowel obstruction.
  20. Subjects requiring treatment with a strong CYP3A inducer are not eligible, unless a transition to an agent with less CYP3A induction is planned ([Appendix D](#)).
  21. Female subject who is pregnant, breastfeeding, or planning to become pregnant while enrolled in this study or within 3 months of last dose of study drug. Male subject who plans to father a child while enrolled in this study or within 3 months after the last dose of study drug.
  22. Unwilling or unable to participate in all required study evaluations and procedures.

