**Appendix E. Child-Pugh Score for Subjects with Chronic Liver Impairment**

Measure	1 point	2 points	3 points
Total bilirubin, µmol/L (mg/dL)	<34 (<2)	34-50 (2-3)	>50 (>3)
Serum albumin, g/L (g/dL)	>35 (>3.5)	28-35 (2.8-3.5)	<28 (<2.8)
PT/INR	<1.7	1.71-2.30	>2.30
Ascites	None	Mild	Moderate to Severe
Hepatic encephalopathy	None	Grade I-II (or suppressed with medication)	Grade III-IV (or refractory)

Points	Class
5-6	A
7-9	B
10-15	C

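### Child-Pugh Class B chronic liver disease with bilirubin at or below 1.5 x ULN is eligible and starts at 420 mg, although the protocol reports an 8.2-fold AUC rise in that class

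*Protocol*

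**What the plan says.** - **Eligibility.** Exclusion 14 in Protocol 4.2 names "Subjects with chronic liver disease with hepatic impairment per Child-Pugh classification Class C" and exempts acute liver dysfunction due to cGVHD. The Synopsis has the same limit. Inclusion 10 defines adequate hepatic function by total bilirubin alone: up to 1.5 x ULN (Gilbert's Syndrome and non-hepatic causes excepted), or above 1.5 "x ULN to 3.0 x ULN if due to GVHD". Inclusion 12 limits PT/INR to below 1.5 x ULN, with INR up to 3.0 allowed on warfarin.
- **Dose.** Section 5.3.1.5 states: "Dose modifications for hepatic impairment will depend on baseline total bilirubin level and subsequent changes in bilirubin levels". Table 3 starts at 420 mg when baseline bilirubin is at or below 1.5 x ULN and at 140 mg when it is above 1.5 and up to 3 x ULN. It raises 140 mg to 420 mg once bilirubin falls to 1.5 x ULN or less. Child-Pugh class does not enter, and Appendix E is used only for exclusion 14.
- **Pharmacology.** Section 1.2.2.1 reports that after a single dose "the AUC of ibrutinib increased 2.7-, 8.2- and 9.8-fold in subjects with mild (Child-Pugh class A), moderate (Child-Pugh class B), and severe" (Class C) hepatic impairment, relative to normal liver function. It adds: "A higher proportion of Grade 3 or higher adverse reactions were reported in patients with B-cell malignancies", in those with mild impairment by NCI criteria. For cGVHD itself it says "there were no differences in ibrutinib exposure between subjects with normal (n=29) and mild hepatic impairment" (n=13, NCI criteria).

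**The concern.** The eligibility limit uses Child-Pugh class and the dose rule uses bilirubin. Between the two lies a group that neither catches: Class B chronic liver disease with bilirubin no higher than 1.5 x ULN. In Appendix E bilirubin is one of five components, so a subject can reach Class B through low albumin and ascites while bilirubin stays low.

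By the protocol's own figures the large step in exposure is from Class A to Class B, yet the line is drawn between B and C. Elsewhere the protocol lowers the starting dose when it expects higher exposure: Table 5 for voriconazole, posaconazole and strong CYP3A inhibitors, and Table 3 for raised bilirubin. This group gets no such reduction.

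What is at stake is the safety of individual subjects. The protocol lists fatal hemorrhage and infections associated with death among the drug's risks (1.2.4.2, 1.2.4.5), and platelets may be as low as 30 x 10^9/L at entry.

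**Working it through.** **Inputs.** AUC ratios from Protocol 1.2.2.1; Child-Pugh points and classes from Appendix E (5-6 = A, 7-9 = B, 10-15 = C); inclusions 10 and 12; Tables 1, 3 and 5. The 8.2-fold figure is an observed result, so there is no formula to reproduce.

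**1. Relative size.** Class B against the excluded Class C: 8.2/9.8 = 0.84. Class B against Class A: 8.2/2.7 = 3.0.

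**2. Bilirubin points.** The documents give no ULN in mg/dL. Assuming 1.0 to 1.3 mg/dL, 1.5 x ULN is 1.5 to 1.95 mg/dL. Both are below 2 mg/dL and score 1 point.

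**3. Can such a subject be Class B?** Take albumin below 2.8 g/dL (3), mild ascites (2), and bilirubin, INR and encephalopathy at 1 each: 3 + 2 + 1 + 1 + 1 = 8, Class B. This subject meets inclusion 10, can meet inclusion 12, and is not removed by exclusion 14.

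**4. Which class results when bilirubin scores 1 point?**

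| INR points | Encephalopathy points | Varied from 1 to 3 | Combinations | A | B | C |
|---|---|---|---|---|---|---|
| 1 | 1 | albumin, ascites | 9 | 3 | 6 | 0 |
| 2 | 1 | albumin, ascites | 9 | 1 | 7 | 1 |
| 3 | 1 | albumin, ascites | 9 | 0 | 6 | 3 |
| 1 | 1 to 3 | albumin, ascites, encephalopathy | 27 | 4 | 19 | 4 |

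INR rows: an assumed INR ULN of 1.1 puts 1.5 x ULN at 1.65 (1 point), and a ULN of 1.2 puts it at 1.8 (2 points). On warfarin, an INR above 2.30 and up to the permitted 3.0 scores 3. The table counts score combinations and says nothing about how often each occurs.

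**5. Dose received.** Table 3 gives the subject in step 3 420 mg. Table 5 lowers this only for voriconazole, posaconazole or another strong CYP3A inhibitor; with a moderate inhibitor the dose stays at 420 mg. After that, Table 3 acts only once bilirubin rises and Table 1 only after toxicity.

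**6. Would a plain change to Class B or C clash with the inclusion criteria?** Yes, in two cases of chronic liver disease with every other component at 1 point, in the order bilirubin, albumin, INR, ascites, encephalopathy:
- Warfarin INR of 2.31 to 3.0: 1 + 1 + 3 + 1 + 1 = 7, Class B, although inclusion 12 admits it.
- Gilbert's bilirubin above 3 mg/dL: 3 + 1 + 1 + 1 + 1 = 7, Class B, although inclusion 10 admits it.

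**7. Power.** With 93 per arm, 30% against 50% and two-sided 5%, power is 0.800, which agrees with Protocol 10.2. Nothing above enters that calculation.

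**The case against.** The case for leaving the plan alone has five parts.

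- **The ratio may not fit these subjects.** It is a single-dose result for Class B as a whole, with no figure for subjects who reach Class B through albumin and ascites alone. Appendices M and N list ascites and nephrotic syndrome among features related to cGVHD, so those points may not always mean lost hepatic clearance. This stands as a limit on the size of the effect. It does not show that exposure is normal, and the documents offer no lower figure for Class B.
- **Other data look reassuring.** The cGVHD comparison covers only NCI-mild impairment. Section 1.2.3.3 found higher exposure with CYP3A inhibitors and no link to dose reductions or discontinuations, but gives no size for that rise, so it cannot vouch for 8.2-fold.
- **Other safeguards exist.** Exclusions 10 and 18 allow an investigator to refuse a subject with a concurrent illness or organ dysfunction, the medical monitor may be consulted on dose reductions, and chemistry is repeated at Week 2 and then every 4 weeks from Week 5 to Week 25. These do narrow the gap, but none has a Child-Pugh trigger. Section 1.2 also refers to the Investigator's Brochure and labeling, whose hepatic guidance cannot be seen here.
- **Enrollment may be over.** SAP 1.1 reports 193 enrolled against about 186 planned. This stands, and it limits the eligibility change.
- **Exclusion 14 might seem empty.** From the first row of the table a reader might infer that it removes nobody whom the inclusion criteria would admit. The documents do not support that. No inclusion criterion bars encephalopathy, and 4 of the 27 combinations are Class C once it varies. With INR at 3 points, 3 of 9 are Class C.

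**Conclusion.** The gap is real and narrow. Under the rules as written, a subject with Class B chronic liver disease and bilirubin at or below 1.5 x ULN enters the trial and starts at 420 mg, in a class whose reported single-dose AUC rise is 8.2-fold, 84% of that in the class the protocol excludes. Only discretionary steps stand in the way. The conclusion rests on the text, on Appendix E scoring, and on an assumed bilirubin ULN of 1.0 to 1.3 mg/dL. The number of subjects affected is not given and is likely to be small. Efficacy, alpha and power are unaffected, so this is a cheap safety improvement.

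Two stronger readings should be avoided. A reader might multiply 420 mg by 8.2, get 3,444 mg, and compare it with the 1,400 mg/day and single 1,680 mg in Section 5.3.1.3. That carries a single-dose ratio far outside the documented proportional range of 420 to 840 mg and is not an exposure estimate. A reader might also infer a safe reduced dose, such as the available 70 mg capsule. At assumed ratios of 3, 6 and 8.2 it corresponds to 210, 420 and 574 mg, too little or too much depending on a steady-state ratio that the documents do not give.

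**What to change.** 1. In Protocol 4.2 and the Synopsis, change exclusion 14 from Class C to Class B or C. Keep the exemption for acute liver dysfunction due to cGVHD. State that INR points due to anticoagulants, and bilirubin points due to Gilbert's Syndrome or a non-hepatic cause, are not counted, so that the criterion agrees with inclusions 10 and 12.
2. Under Table 3, add a note for any subject on treatment with known Class B chronic liver disease: hold ibrutinib/placebo and obtain medical monitor review before any further dosing, with no step-up to 420 mg on bilirubin alone. Set no fixed reduced dose.

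**Cost.** An edit to one criterion in two places and one note. Screening needs nothing new, since exclusion 14 already requires the Child-Pugh class and PT/INR is measured then. PT/INR is not scheduled later, so re-scoring a subject whose chronic liver disease worsens would need a local INR. The note applies to ibrutinib and placebo alike, so the blind is kept. Eligibility becomes slightly narrower and the trial yields no Class B data. Item 1 acts only before or during enrollment; item 2 can still protect a subject on treatment.

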**Table 3. Ibrutinib/Placebo Dose Modifications for Subjects with Hepatic Impairment**

Starting Dose Level by Bilirubin Levels	Bili <math>\leq 1.5</math> x ULN at baseline: 420 mg	Bili <math>> 1.5-3</math> x ULN at baseline: 140 mg
On-study bilirubin level $\leq 1.5$ x ULN	Continue 420 mg	Increase to 420 mg
On-study bilirubin level $> 1.5-3$ x ULN	Reduce to 140 mg	Continue 140 mg
On-study bilirubin level $> 3$ x ULN	
 
Hold* until bili level <math>> 1.5-3</math> x ULN restart at 140mg
 
When bili level <math>\leq 1.5</math> x ULN restart at 420mg
 
	
 
Hold* until bili level <math>> 1.5-3</math> x ULN restart at 140mg
 
When bili level <math>\leq 1.5</math> x ULN restart at 420mg
 

Bili = bilirubin

\* In cases where the investigator wishes to restart ibrutinib/placebo after ibrutinib/placebo has been held for more than 28 days for hepatic impairment, please contact the medical monitor for approval.

In the event a patient has had a dose reduction due to a non-hepatic toxicity and then develops elevated bilirubin level (or vice versa) that requires a dose reduction, the lower of the two dose reductions should be used. The medical monitor should be consulted for any questions involving dose reductions.

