### 5.3.1.2. Dose and Administration

Ibrutinib or placebo is administered orally once daily. It is expected that many subjects commencing therapy with high dose prednisone will require anti-fungal prophylaxis. Please see [Section 6.2.1](#) for dose modification guidelines with concomitant use of CYP3A inhibitors or inducers.

The capsules are to be taken around the same time each day with 8 ounces (approximately 240 mL) of water. The capsules should be swallowed intact and subjects should not attempt to open capsules or dissolve them in water. If a dose is not taken at the scheduled time, it can be taken as soon as possible on the same day with a return to the normal schedule the following day. The subject should not take extra capsules to make up the missed dose.

The first dose will be delivered in the clinic on Day 1, after which subsequent dosing is typically on an outpatient basis. Ibrutinib will be dispensed to subjects in bottles at each visit. Unused ibrutinib dispensed during previous visits must be returned to the site and drug accountability records ([Section 12.8](#)) updated at each visit. Returned capsules must not be redispensed to anyone.

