**Table 5. Ibrutinib/Placebo Dose Modifications for Concomitant Use of CYP3A Inhibitors**

CYP inhibitor class	Dose modification instructions

 
Mild CYP3A inhibitors
 
	420 mg once daily. No dose adjustment required.

 
Moderate CYP3A inhibitors
 
	420 mg once daily. No dose adjustment required.

 
Voriconazole at any dose or
 
Posaconazole at doses less than or equal to suspension 200 mg BID or delayed-release tablet 300 mg QD
 
	280 mg once daily

 
Strong CYP3A inhibitors or
 
Posaconazole at higher doses
 
	140 mg once daily or consider alternative with less CYP3A inhibitory potential

Avoid concomitant use of strong CYP3A inducers ([Appendix D](#)). Consider alternative agents with less CYP3A induction and transition to a new agent within 4 weeks of randomization.

A list of common CYP3A inhibitors and inducers is provided in [Appendix D](#). For further information, please refer to the current version of the ibrutinib [IB](#) and examples of inhibitors, inducers, and substrates can be found at <http://medicine.iupui.edu/clinpharm/ddis/main-table/>. This website is continually revised and should be checked frequently for updates.

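### Tables 3 and 5 assign different ibrutinib/placebo doses to a subject whose dose changes for bilirubin while on a CYP3A inhibitor that Table 5 adjusts for, and no rule says which governs

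*Protocol*

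**What the plan says.** Protocol Section 5.3.1.5 opens: "Dose modifications for hepatic impairment will depend on baseline total bilirubin level and subsequent changes in bilirubin levels per" Table 3. That table has one column for baseline bilirubin up to 1.5 x ULN (starting dose 420 mg) and one for above 1.5 and up to 3 x ULN (starting dose 140 mg). On study:

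- At or below 1.5 x ULN, the cells read "Continue 420 mg" and "Increase to 420 mg" respectively.
- Above 1.5 and up to 3 x ULN, a subject who started at 420 mg gets "Reduce to 140 mg", and one who started at 140 mg stays there.
- Above 3 x ULN, drug is held. It restarts at 140 mg in the middle band and at 420 mg once bilirubin is at or below 1.5 x ULN.

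Protocol Section 6.2.1, Table 5, assigns doses by inhibitor and does not mention bilirubin. Mild and moderate inhibitors need no adjustment from 420 mg. Voriconazole at any dose, or posaconazole up to a stated dose, gives 280 mg. For strong inhibitors or higher-dose posaconazole it says "140 mg once daily or consider alternative with less CYP3A inhibitory potential".

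Three other texts bear on how these combine. The note under Table 2 sends the reader to both sections. The text under Table 3 says that "the lower of the two dose reductions should be used" when a reduction for a non-hepatic toxicity coincides with one for raised bilirubin, in either order. It also refers questions about dose reductions to the medical monitor.

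**The concern.** Both tables state absolute doses, each keyed to a different variable, and neither refers to the other. A subject can fall under both at once, and a site that follows a stated cell in one table can then give a dose that the other contradicts.

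The overlap is foreseeable. Inclusion criterion 10 admits bilirubin up to 3.0 x ULN when it is due to GVHD, which fills the right-hand column of Table 3. Section 5.3.1.2 says: "It is expected that many subjects commencing therapy with high dose prednisone will require anti-fungal prophylaxis". The footnote to Appendix D replaces itraconazole and ketoconazole with voriconazole, which puts those subjects in the 280 mg row of Table 5.

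At stake is whether subjects in the same clinical situation get the same dose at different sites. Two existing checks would not show a discrepancy. Section 5.3.1.3 counts only doses above 420 mg as overdose, and SAP Section 3.4 lists dose reductions due to adverse events but no changes made for bilirubin or for an inhibitor.

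**Working it through.** No stated figure in the plan needs reproducing here. The check is to cross the two tables and compare the doses.

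**Inputs.** Table 3, when drug is being given: 420 mg at bilirubin ≤1.5 x ULN and 140 mg at >1.5 to 3 x ULN. Table 5: 280 mg and 140 mg for the two groups of inhibitors that it adjusts for. Ratio = larger dose / smaller dose.

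| On-study bilirubin | Inhibitor | Table 3 | Table 5 | Ratio |
|---|---|---|---|---|
| ≤1.5 x ULN | voriconazole, lower-dose posaconazole | 420 mg | 280 mg | 420/280 = 1.5 |
| ≤1.5 x ULN | strong, higher-dose posaconazole | 420 mg | 140 mg | 420/140 = 3.0 |
| >1.5 to 3 x ULN | voriconazole, lower-dose posaconazole | 140 mg | 280 mg | 280/140 = 2.0 |
| >1.5 to 3 x ULN | strong, higher-dose posaconazole | 140 mg | 140 mg | 1.0 |

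Three of the four combinations disagree, and not all in the same direction. Table 3 gives the higher dose in the first two rows and the lower dose in the third.

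**Two subjects traced through the tables.**

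1. Baseline bilirubin 2 x ULN due to GVHD, on voriconazole. At the start, Table 3 gives 140 mg and Table 5 gives 280 mg. When bilirubin falls to ≤1.5 x ULN, Table 3 gives 420 mg and Table 5 gives 280 mg.
2. On a strong inhibitor at 140 mg, then held for bilirubin >3 x ULN. In the middle band both tables give 140 mg. At ≤1.5 x ULN, Table 3 restarts at 420 mg and Table 5 gives 140 mg.

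**Does any other text settle it?**

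- The note under Table 2 names both sections but gives no precedence.
- The tie-break is triggered by a non-hepatic toxicity plus raised bilirubin. An adjustment for an inhibitor is not a toxicity, and an increase or a restart at 420 mg is not a reduction. By its wording the rule does not reach this pair.
- The medical-monitor sentence concerns questions on reductions and states no dose rule.

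**How many subjects?** The documents do not say. In the earlier cGVHD study (Section 1.2.3.3, N = 42), 14.3% took voriconazole (6/42) and 9.5% posaconazole (4/42). Suppose that use carries over to the 193 subjects enrolled (SAP Section 1.1). Voriconazole alone gives 193 × 6/42 = 27.6. Both drugs with no overlap give 193 × 10/42 = 46.0. So about 28 to 46 subjects, in both arms together, would take one of these two azoles. The conflict affects only those who also have a bilirubin-driven dose change, and that share is not given.

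**The case against.** The strongest reply is that this is a missing sentence with a safeguard behind it. The note under Table 2 and Section 5.3.1.2 both direct sites to the CYP3A section, so a careful site would open both tables, and the medical monitor can be asked. That stands in part: sites are told that both adjustments exist. They are not told how to combine them, and a cell that instructs an increase or a restart does not look like a question about a reduction.

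The 3-fold gap is also fairly called narrow. It needs a strong inhibitor or higher-dose posaconazole. The Appendix D footnote moves itraconazole and ketoconazole users to voriconazole, and Table 5 itself suggests considering another agent.

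Several stronger readings are tempting, and the documents do not support them:

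- *Every subject on these azoles is affected.* Table 3 is for hepatic impairment, and Section 5.3.1.5 exempts Gilbert's Syndrome and non-hepatic causes. A subject with no bilirubin-driven change has no need of it. The 28 to 46 above is the pool from which conflicts could arise.
- *The tables also conflict for mild or moderate inhibitors* (140 against 420 mg in the middle band). Table 5 asks for no adjustment there, so it can be read as leaving the bilirubin dose alone.
- *A subject on a strong inhibitor at 140 mg gets no reduction when bilirubin rises to the middle band.* Both tables say 140 mg, so there is no contradiction. Whether a further reduction is needed is a clinical question.
- *Table 2 fails because it is keyed to "Starting Dose Level".* It has separate 280 mg and 140 mg columns, and Table 1 words its step relative to the dose in use.
- *The tie-break could mean the smaller reduction, hence the higher dose.* That reading is strained.
- *The conflict adds toxicity-driven stops.* Section 1.2.3.3 reports higher exposure with moderate and strong inhibitors, but no association with dose reductions or discontinuations. Section 1.2.2.1 reports no exposure difference between normal and mildly impaired liver function in the Phase 2 cGVHD study (n = 29 and 13). These samples are small, but nothing in the documents shows the opposite. They also do not settle which table a site must follow.

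**Conclusion.** The contradiction is real and limited to Tables 3 and 5. For a subject with a bilirubin-driven dose change while on an inhibitor that Table 5 adjusts for, the stated doses are:

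- 1.5-fold apart (420 against 280 mg) on recovery with voriconazole or lower-dose posaconazole;
- 3-fold apart (420 against 140 mg) on recovery with strong inhibitors or higher-dose posaconazole, a narrower group;
- 2-fold apart in the other direction (140 against 280 mg) in the middle bilirubin band with voriconazole or lower-dose posaconazole.

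This rests on reading the cells as written and on the absence of any precedence text; the ratios need no outside figure. The number of subjects affected cannot be derived from the documents. No effect on toxicity, type I error, power or the primary comparison is shown. It still matters, because explicit dosing instructions contradict each other in a situation that the protocol itself makes foreseeable. That is more than missing detail.

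**What to change.** Reconcile Table 3, Table 5 and the tie-break sentence under Table 3 in one amendment. State one rule for when adjustments for bilirubin, CYP3A inhibitor and toxicity coincide. Word it as the resulting dose, and make it cover increases and restarts as well as reductions. Put a cross-reference to the rule in both tables. The sponsor's clinical and pharmacology team decides the doses and which passage governs; this review takes no position on either.

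The SAP reports enrolment as complete, so the amendment helps only subjects still on study drug. Sites with such subjects should be notified directly.

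The cost is protocol wording and a site memo. No new subjects or assessments are needed, and the analysis does not change.
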